4.2 Model and Design

[figure not shown]
Figure 4.2.1 illustrates the pathway through which the behavioral (provider-level) and implementation (practice-level) interventions are intended to result in improved receipt of dental care. The theory-driven interventions were developed using two frameworks: socio-ecological (McLeroy et al., 1988; Sallis and Owen, 2002) and intervention mapping (Bartholomew & Mullen, 2011). Thus, on a provider-level, pediatricians' and nurse practitioners' communication of OH facts + prescription along with list of dentists are intended to change parental caries illness perception (from disjointed inaccurate → chronic organized understanding) and are intended to change self-efficacy to seek dental care for their child. On a practice level, the integration of oral health and systematic documentation in EMR supports uniform data collection and enhances continuous quality improvement to facilitate providers' follow-up with the parent at the next WCV.

Study measures/evaluations (See Table 8.1.1) will utilize the RE-AIM framework (Glasgow et al., 2001; Glasgow et al., 1999) similar to a hybrid designed study (Cully et al., 2014). Internal validity is assessed by effectiveness and implementation/fidelity; external validity is assessed by

reach, adoption, and maintenance (See Figure 4.2.1). Child primary (i.e. dental attendance) and secondary (i.e. development of new caries, changes in oral hygiene, frequency of sweetened food and drinks, oral health-related quality of life, and dental costs) effectiveness outcomes will be mediated by changes in parent's illness perception and self-efficacy. Other external validity outcomes as a result of provider- and practice-level interventions via mediators (provider's OH knowledge and self-efficacy; practice's leadership completing the organization readiness, climate, and attitude questionnaire) will also influence the child outcomes. A literature search on the predictors of dental attendance identified moderating variables such as caregivers' sociodemographics (Ismail et al. 2003), health literacy (Vann et al., 2013), social support (Duijster et al., 2014; [name] et al., 2012) and child medical illness as a confounder (Chi et al., 2011; Chi & Rakljos, 2012). Thus, all measures and evaluations collected for this study will follow the conceptual model.

For the purposes of dissemination of cRCT study results and the intervention components to all stakeholders, the study will utilize Roger's Diffusion of Innovation3 framework for evaluation and development of a toolkit. Specifically, process outcomes collected as part of implementing the cRCT together with additional structured interview data (to be collected from participating providers) on barriers/enablers will help in understanding the characteristics of the intervention and any changes that would need to be made for dissemination purposes.

Figure 4.2.1 Conceptual model describing the pathway mechanisms of the behavioral- (provider) and implementation- (practice) level interventions

Interventions to be tested:

Arm A (N = 512): Practices will receive interventions at the provider and practice levels.

Provider-level interventions will be: Common-Sense Model of Self-Regulation (CSM) based education and skills training for the provider to teach him/her to communicate core oral health facts to parents, provide a prescription to take their child to the dentist together with a list of Medicaid-accepting dentists in the area, and document the oral health encounter in EMR.

Practice-level interventions will be: Enhancements to the EMR system to include oral health documentation (four questions) which will be implemented prior to enrolling any parent/caregiver and child participants into the study.

Arm B (N = 512): Enhanced usual care (AAP based) at the provider level, no practice level intervention.

Providers in these practices will receive American Academy of Pediatrics (AAP) based oral health education and follow the usual care for oral health assessment recommended by AAP guidelines. The AAP based education is unlike the CSM based intervention education (given to Arm A) in that it is not theory based to provide understanding of the chronicity of dental caries.

4.3 Design of Supplementary Objective 3.3

Qualitative data collection to evaluate dissemination strategies to translate trial results and resources to all stakeholders will also be completed. Specifically, we will use the final trial results, the process outcomes collected during the study, and additionally collect structured interview data from participating providers on implementation barriers/enablers to evaluate best strategies for dissemination of the oral health intervention. In addition to disseminating trial results, a tool kit will also be developed to translate the evidence based intervention among all primary care stakeholders.

The 63 participating providers will be asked to participate in a structured interview to assess the characteristics of the intervention and implementation barriers/enablers according to Roger's Diffusion of Innovation framework. These interviews will be collected from the providers after the completion of all parent/caregiver-child dyad WCV3 visits. A trained moderator will conduct the interviews (\approx 45 minutes) at the practices to assess the following: 1) relative advantage of the OH intervention; 2) compatibility of the OH intervention with the needs of the adopters; 3) Complexity of the OH intervention; 4) Trialability, i.e. implementing the OH intervention without a large investment; 5) observability, i.e if the results of the OH intervention are noticeable to parents and providers. The table below gives the list of questions that will be asked under each domain. All interviews will be audio-taped. Audio tapes from the interviews will be transcribed, and then coded in Atlas.ti, a software program which allows for the analysis of qualitative data. Analysis will be supervised by Drs. [name] who has experience conducting qualitative work. A detailed summary of the ideas for implementation strategies and development of the tool kit will be produced. Interviews with providers will be conducted using zoom if in-person interviews are not possible due to the current COVID-19 outbreak.

Diffusion of Innovations Theory Characteristics	Structured interview Questions for Providers
(1) Relative advantage: the degree to which the innovation is viewed as better than the previously available ideas or programs.	Is the information in the didactic oral health (OH) curriculum you received as part of training better than the ones available on professional websites (ADA, AAP, and AAPD)? a. Was anything new presented? b. Did you learn anything? Can the curriculum with the OH facts be delivered successfully to parents? Should the training be made available from experts? a. Has skills training been helpful? b. Does it give confidence in delivery? c. Is in-person training necessary?
(2) Compatibility: the degree to which the innovation is consistent with the values, experiences, and needs of potential adopters.	Are the OH activities in primary care compatible with physicians/NP's goal of quality of care delivery? a. What are the enablers? b. What are the barriers?

(3) Complexity: How difficult the innovation is to understand or how complex it is to use.	Are the OH activities simple to be followed in practice settings? a. What could be made simpler? b. What works and what does not?
(4) Triability: the degree to which the innovation can be experimented with on a limited basis without a large investment.	Has the implementation of OH activities been cost-effective?
(5) Observability: the degree to which the results of an innovation are visible to others.	Do you think the OH activities have helped your parents to take their child to the dentist and also helped with Quality Improvement in your practice?

5 STUDY ENROLLMENT AND WITHDRAWAL

5.1 Subject Inclusion Criteria

In order to be eligible to participate in this study, all of the following criteria must be met:

Practices:

- Use Electronic Medical Record (EMR)
- Have \geq 20% of pediatric patients covered by Medicaid Providers:
- Pediatrician or Nurse Practitioner with a minimum of 2 patient-care days per week
- Provide signed and dated consent form Parents or caregivers:
- Legal guardianship of Medicaid-enrolled children aged 3-6 years attending well-child visit (WCV)
 - Must be \geq 18 years
 - Speak English or Spanish
 - Provide signed and dated consent form
 - Planning to stay in the immediate area (both parent/caregiver and child) for at least two years Child:
 - Ages 3-6 years
 - Enrolled in Medicaid

5.2 Subject Exclusion Criteria

An individual who meets any of the following criteria will be excluded from participation in this study:

Child:

- Presence of any serious medical or behavioral condition (e.g. cerebral palsy, autism) that precludes participation in the dental screening

5.3 Strategies for Recruitment and Retention

Practices:

During the pilot study phase, Medical Directors from the 26 RCC practices were invited to participate in an informational webinar led by the PI and a Co-Investigator (Medical Director of the RCC) to learn more about the opportunity for their practice to participate in the study. The PI, Project Manager and Study Coordinator then met with interested providers at practices which met the inclusion criteria. The 18 practices which met the inclusion criteria have provided letters of support indicating their commitment to participation. One practice will serve as a backup practice and has also given a letter of support.

Retention strategies for the practices will include regular contact between the study staff and practice staff to ensure any issues which may arise are addressed immediately, and tailoring study logistics based on practice flow as learned from our two pilot practices.

Practices also receive compensation for facility use for the trainings, for research staff being present at the practices to complete study visits, and for the structured interviews and debriefing sessions.

Providers:

During the pilot study phase, all pediatricians and nurse practitioners of the 18 practices were invited to attend the informational meetings which took place at their individual practices. The PI, Project Manager and Study Coordinator briefed the providers regarding the study goals and logistics. A total of 67 providers from the 18 practices to be randomized who met the inclusion criteria will participate in the main trial. An additional information session for providers will be held at each practice prior to the start of the main trial. At this time, informed consent will be obtained from each pediatrician/nurse practitioner participant.

Retention strategies for providers include Continuing Medical Education (CME) credits for didactic OH education and Maintenance of Certification (MOC) credits for quality improvement initiatives. Twenty five (25) MOC credits have been approved by the American Academy of Pediatrics (AAP) for physicians participating in this dental project. The study staff will maintain regular contact with providers to address any concern or issue that may arise.

CME credits will also be available for providers upon completion of briefing seminar.

Parent/caregivers:

All parents of 3-6 year-old Medicaid-enrolled children attending a WCV in the selected practices during the recruitment period will be invited to participate in the study. Based on the data from the 18 practices, we expect 7,421 Medicaid-enrolled children aged 3-6 years to have a WCV at the pediatric offices per year. In our pilot study, the participation rate was 95%, hence similar strategies will be implemented in the main trial.

A team consisting of a research assistant and dental hygienist will be assigned to one practice at a time to be on-site daily for recruitment of caregiver-child dyads at larger practices. A floating team will recruit at multiple smaller practices simultaneously. The available sample pool for the 3-month recruitment period is 1,855 (25% of 7,421). We anticipate that 5% will be ineligible based on inclusion and exclusion criteria, thus reducing the potential sample to 1,762 (95% of 1,855). Based on our experiences recruiting and enrolling parent/caregivers in 2 pilot practices,

we expect a participation rate of 95% (of 1,762), giving us an available potential sample size of 1,674 per 6 practices enrolled. For the total of 18 practices, we can expect a potential sample size of 5,022 from whom we can recruit the target sample size of 1024 participants (512 per arm for 2 arms) required to test the hypothesis of the study. Therefore, our goal of recruiting 56 to 57 participants per practice given the potentially large population pool of each practice is an achievable approach to meet the main trial sample size. The recruitment is expected to be completed within a 9-month time frame.

The recruitment and enrollment strategies proved to be effective in the pilot study will be used for the main trial as follows:

- When making appointment reminder calls, practice staff will give a brief overview of the study (using a recruitment script) and ask caregivers to come early to fill out the consent forms and questionnaires.
- Tailored to the practice's or provider's preference, the medical assistant may approach caregivers first, before study staff explain and obtain consent. An alternative approach is that study staff will approach caregivers in the waiting room.
- All 3 questionnaires, i.e. Illness Perception Questionnaire-Revised for Dental (IPQ-RD), Parent Questionnaire, and Parent Exit Questionnaire, can be completed on paper or tablet according to the caregiver's preference.
- At each WCV, study staff will give caregivers an incentive (i.e. cash or gift card) and a small gift for their child for completing the study visit questionnaires.

Retention strategies for parent/caregivers, lessons learned from the pilot study and best practices identified in the literature will be followed as below:

- Parents/caregivers will be given promotional items (i.e. pens, magnets) with the study logo and contact phone number at recruitment.
- Alternate contact information for family/friends that may be able to reach the participant if primary contact information becomes invalid will be obtained at recruitment.
- Annual birthday/holiday cards will be sent to parent and child participants to maintain contact.
- Newsletters will be sent twice a year with updates on the study's progress (i.e. recruitment), and a reminder to update their contact information (by phone or mail).
- Study staff will contact parents/caregivers during follow-up to remind them to schedule and attend their annual WCV.
- Assistance from practice staff will also be solicited for hard to reach/contact participants.

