4 STUDY DESIGN

This study will utilize a multi-site, multi-level, and multi-component cluster randomized clinical trial design (Phase III) to assess interventions intended to address poor dental utilization (attendance) and untreated caries among 3-6 year old Medicaid-enrolled children attending well-child visits (WCV) in primary care settings. The focus is on addressing factors (determinants) at the socio-ecological levels of the child's environment: provider (pediatrician and nurse practitioner), parent/caregiver and practice/organization levels. Eighteen practices will be randomized to 2 arms for provider training and practice/organization level study intervention changes: A) provider-level CSM training, provision of oral health facts to parents, a prescription and a list of dentists accepting Medicaid + practice-level EMR changes for documenting oral health; B) AAP training with no prescription or list of dentists accepting Medicaid and no changes to the EMR. Arm A parents/caregivers will receive oral health facts and prescription to take their child to the dentist and improve oral health behaviors in the home, while Arm B parent/caregivers will receive usual AAP-based care for oral health. Each arm will consist of 9 practices (n= 18), 33 to 34 providers (n= 67), and 512 parent/caregiver and child dyads (n= 1024). Each parent/caregiver and child dyads will be recruited at the first WCV and then followed for two consecutive WCVs (for a 24 month duration or until the subject has completed 3 well child visits). Each provider will complete the didactic and skills training prior to enrolling any parent/caregiver and will participate in the study for a total of 24 months duration (includes initial and booster didactic and skills training: 3 months, WCV#1: 3 months, WCV#2: 3 months, WCV#3: 3 months). Data will be collected prior to WCVs, at WCVs, and follow-up visits.

Immediately after randomization of practices, recruitment will be rolled-out, i.e. parent/caregivers will be recruited during a 3-month period in 6 practices at a time, with recruitment at all 18 practices expected to be completed in 9 months. This strategy will maximize staff time and ensure that EMR integration of OH is complete at practices randomized to Arm A, and that providers receive the didactic and skills training prior to their practice's rollout.

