4.1 Study participants

Subjects will be pediatric providers (Pediatricians/Nurse Practitioners) and parent/caregivers and their 3-6 year old children from 18 primary care practices located in Ashtabula, Cuyahoga, Geauga, Lorain, Medina, and Portage counties in Ohio (see Table 4.1.1 below). One additional practice not included in the table, Premier Pediatrics, has also agreed to participate and will be included if needed to replace a practice. The majority of the practices are in Cuyahoga County (67%) and the remaining 33% are in surrounding counties in NE Ohio. All practices serve $\geq 20\%$ Medicaid eligible children (9 practices with 20-40% and 9 practices with $> 40\%$ Medicaid-eligible children) and are from the Rainbow Care Connection (RCC). The study is offered to all pediatricians/nurse practitioners in the recruited practices and will be offered to all eligible caregivers and their children excluding those with serious medical or behavioral conditions which would preclude them from participating in the dental screening. All provider and parent participants meeting the eligibility criteria will be enrolled in the study upon signing the consent form.

Table 4.1.1 Practice Information

Practice/Site	# Pediatricians	# Nurse Practitioners	Medicaid Patients (age 3-6)	Medicaid Patients w/WCV (age 3-6)	% Medicaid	County
Ashtabula Pediatrics	1	2	592	448	63%	Ashtabula
Chardon Pediatrics	4	1	387	267	34%	Geauga
Elyria Pediatric Care	3	0	205	168	33%	Lorain
Healthy Kids Pediatrics	1	1	121	95	31%	Portage
[name]	1	0	344	340	80%	Cuyahoga
Medina Pediatrics	4	2	338	250	23%	Medina
NEON	5	0	1856	357	80%	Cuyahoga
Otis Moss	2	0	297	233	82%	Cuyahoga
Pediatric and Adolescent Health Professionals	3	0	157	118	22%	Cuyahoga
Pediatric Partners of Cleveland	2	0	209	165	40%	Cuyahoga
Pediatric Services - Parma	8	0	740	588	30%	Cuyahoga
Pediatriccenter – Garfield	2	0	561	384	24%	Cuyahoga
Rainbow Ambulatory Clinic	4	0	2728	2361	86%	Cuyahoga
Rainbow Euclid Pediatrics	1	0	246	186	68%	Cuyahoga
Suburban Pediatrics - Shaker	7	0	408	335	23%	Cuyahoga
University Premier Pediatricians – Euclid	4	1	504	418	49%	Cuyahoga
UH Westshore Primary Care **	4	0	424	185	45%	Cuyahoga
University Pediatrics of Lorain	4	0	653	523	61%	Lorain
Totals	60	7	10,302	7,421		

Practice information data captured 1/1/2016 through 12/31/2016.

**Data captured 1/1/2017 through 5/31/2017

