7.2 Parent/Caregiver and Child

7.2.1 Baseline Visit: WCV #1

At WCV #1 (T₀: Day 0)

Before Provider Encounter

- Study Staff will recruit 1024 parent/caregivers and their children from the 18 practices (approximately 56-57 participants/practice) using an in-person approach. Parents/caregivers attending well-child visits with 3-6 year old children will be approached for participation.

- In the waiting area/exam room of the pediatric practice, study staff will review inclusion/exclusion criteria as outlined on the screening survey to determine parent/caregiver and child eligibility (Refer to Sections 5.1, 5.2).
- Review the written consent form with the potential participant; study staff signs the consent form acknowledging that informed consent was reviewed and caregiver signs acknowledging consent was obtained (Appendix C: Consent forms).
- In the waiting area/exam room of the pediatric practice, study staff will obtain contact information.
- In the exam room, caregivers will complete the following self-administered Baseline questionnaires: A1: Illness Perception Questionnaire-Revised for Dental (IPQ-RD) and A2: Parent Questionnaire (Appendix E: Questionnaires & forms).
- In the exam room, dental hygienist will perform child dental screening examination and study staff will record results of the dental screening examination. Results will not be available to the provider, unless the hygienist finds that the child has urgent needs that require immediate attention. (Appendix E: Questionnaires & forms).

During Provider Encounter in the Exam Room

- Caregivers attending WCV's will receive OH information, prescription to take the child to the dentist + list of local Medicaid-accepting dentists from provider, based on study arm.
- Caregivers attending WCV's may have study staff audiotape or directly observe the provider encounter to evaluate provider's delivery of OH communication (for a sample of visits).

After Provider Encounter in the Exam Room/Waiting Area

- Caregivers will provide feedback about the OH information given to them during the medical visit with a short self-administered exit questionnaire (A3: [Appendix E: Questionnaires & forms]).
- Caregivers will be given the B1: Follow-up IPQ-RD (Appendix E: Questionnaires & forms) to be completed and returned (in postage paid envelope or in person, based on participant preference).

After WCV #1 (T₁)

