The primary objective is to compare dental care attendance between the two arms. For simplicity in the power calculation we consider the binary outcome of any dental attendance in the two year period of follow-up. Dental attendance will be based on a single summary score (number of years - out of two - in which the child visits the dentist at least once a year). We thus suppose the use of a two-sided 0.05 alpha level z test (with pooled variance) for a difference in proportions. We assume, as a rough approximation, that the study will recruit an equal number of patients in each practice. Making conservative allowances for an intra-cluster (within-practice) correlation (ICC: in the binary dental attendance outcome) of 0.04 and a 25% drop-out rate, a sample size of 512 participants per arm (total n= 1024) will provide an estimated 80% power to detect the above difference in proportions. Alternatively, this sample size (actually 438 per group) will provide 90% power to detect this same effect size if the ICC is only 0.02. If the intervention effect is only 0.12 (0.42 versus 0.30), a sample size of 457 per group (914 total) will still provide 80% power with a dropout rate of 25% if the ICC is only 0.01. For the purposes of this study, a sample size of 512/arm (n=1024) will be recruited.

For sample size estimates, an important secondary outcome will be incidence of new decayed or filled teeth (dft). Mean dft is hypothesized to decrease for Arm A relative to Arm B. Our

previous data (Lee et al. 2015) among 5 to 7 year old low-income children suggests a mean dft for usual care of 4.5 (standard deviation = 7) which we assume to be a reasonable value for the enhanced usual care arm in the present study. We assume the same standard deviation for the new intervention group, assuming normally distributed responses for the power calculation. In fact, as dft is a count (possibly following a distribution such as Poisson or negative binomial) it is likely that the standard deviation will decrease with the mean, making our approach conservative (McCullagh and Nelder 1989).

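### Section 5.3 counts the recruitment pool three times (5,022 instead of about 1,674), and six to eight practices cannot reach the uniform 56-57 on the stated schedule

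*Combined protocol and SAP*

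**What the plan says.** Section 5.3 starts from an annual count: "Based on the data from the 18 practices, we expect 7,421 Medicaid-enrolled children aged 3-6 years to have a WCV" each year. It takes 25% of this for a 3-month recruitment period (1,855), removes 5% as ineligible (1,762) and applies 95% participation, "giving us an available potential sample size of 1,674 per 6 practices enrolled". It then concludes: "For the total of 18 practices, we can expect a potential sample size of 5,022". From this it infers that "our goal of recruiting 56 to 57 participants per practice given the potentially large population pool of each practice is an achievable approach". Section 7.2.1 repeats the figure as "approximately 56-57 participants/practice".

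The schedule is in section 4: "parent/caregivers will be recruited during a 3-month period in 6 practices at a time", with all 18 practices expected to finish in 9 months. The practice volumes are in Table 4.1.1 (section 4.1), whose footnote reads "Practice information data captured 1/1/2016 through 12/31/2016". A second footnote says that the UH Westshore row covers January to May 2017 only.

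On cluster size, section 12.2 states: "We assume, as a rough approximation, that the study will recruit an equal number of patients in each practice".

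**The concern.** The 7,421 visits belong to all 18 practices, so a figure derived from them by percentages alone also belongs to all 18. Attaching it to six practices and tripling it counts every practice three times.

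Section 5.3 exists to show that the target can be met. If the pool is one third of the stated size, the margin is much thinner than a reader would think. The argument that every practice has a large pool also has to be checked practice by practice, because volumes in Table 4.1.1 run from 95 to 2,361 visits. If small practices cannot reach 56-57, the equal cluster sizes behind the power in section 12.2 cannot be obtained on the stated schedule, and the quoted 80% is somewhat high.

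**Working it through.** **1. The plan's own figure.** The 18 rows of the well-child-visit column in Table 4.1.1 sum to 7,421.

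- 7,421 × 0.25 = 1,855
- 1,855 × 0.95 = 1,762
- 1,762 × 0.95 = 1,674
- 1,674 × 3 = 5,022

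The chain reproduces, but every step before the last concerns 18 practices.

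**2. Could 1,674 belong to six practices?** An average six would give 1,674 / 3 = 558. The six largest give 1,065. Neither comes near 1,674. The 5,022 would be right only if every practice recruited for nine months (7,421 × 0.75 × 0.9025 = 5,023), which is not the schedule in section 4.

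**3. Corrected pool.** It is 1,674 with the table as printed. Annualising UH Westshore (185 × 12/5 = 444, an assumption) makes the visit total 7,680 and the pool 1,733.

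- 1,024 / 5,022 = 20% (as the plan implies)
- 1,024 / 1,674 = 61%
- 1,024 / 1,733 = 59%

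**4. Capacity per practice in one 3-month window** = annual visits × 0.25 × 0.95 × 0.95.

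| Practice | Visits | 3-month capacity |
|---|---|---|
| Healthy Kids Pediatrics | 95 | 21.4 |
| Pediatric and Adolescent Health Professionals | 118 | 26.6 |
| Pediatric Partners of Cleveland | 165 | 37.2 |
| Elyria Pediatric Care | 168 | 37.9 |
| UH Westshore | 185 (444 annualised) | 41.7 (100.2) |
| Rainbow Euclid Pediatrics | 186 | 42.0 |
| Cuyahoga practice with 233 visits | 233 | 52.6 |
| Medina Pediatrics | 250 | 56.4 |

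Seven practices are below 56 and eight below 57 as printed; six and seven with Westshore annualised. Rainbow Ambulatory Clinic alone supplies 532.7 of the 1,674 (32%).

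**5. What recruitment could look like.** Let each practice recruit the smaller of its capacity and a common ceiling.

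- *Larger practices make up the shortfall:* a ceiling of about 72 (69 annualised) gives 1,024 in total, with coefficient of variation (CV) of cluster size 0.306 (0.282).
- *Every practice stops at 57:* 886 in total (901), which is 12-13% short of 1,024, with CV 0.231 (0.227).

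**6. Power.** Inputs from section 12.2: 0.46 versus 0.30, two-sided 0.05 z test with pooled variance, ICC 0.04, 25% dropout, 9 practices per arm.

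- Design effect DE = 1 + ((1 + CV²) × m − 1) × ICC, where m is mean completers per practice.
- Effective n per arm = completers per arm / DE.
- Power = Φ[(0.16√n − 1.96√(2 × 0.38 × 0.62)) / √(0.46 × 0.54 + 0.30 × 0.70)].

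Equal clusters: m = 1,024 × 0.75 / 18 = 42.67; DE = 1 + 41.67 × 0.04 = 2.667; n = 384 / 2.667 = 144; power = Φ[(1.920 − 1.345) / 0.677] = 0.802. This reproduces the stated 80%.

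| Scenario (Westshore annualised in brackets) | DE | Effective n per arm | Power, ICC 0.04 |
|---|---|---|---|
| Equal clusters, 1,024 | 2.667 | 144 | 0.80 |
| Larger practices fill to 1,024 | 2.826 (2.802) | 135.9 (137.0) | 0.775-0.779 (0.779-0.782) |
| Stop at 57 each | 2.515 (2.539) | 132.1 (133.1) | 0.764-0.767 (0.767-0.770) |

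The lower end of each range uses the pooled variance under the alternative as well. At ICC 0.02 and 512 per arm, power is 0.92 with equal clusters, 0.91 with filling and 0.89-0.90 with the stop at 57.

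**The case against.** The overcount does not overturn the conclusion that it supports: 1,674 still exceeds 1,024, and neither the randomisation nor the analysis uses 5,022. That stands.

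No rule in the plan closes a practice after three months, and section 5.3 provides a floating team for the smaller sites. At the plan's rates the smallest practice recruits 95 × 0.9025 / 12 = 7.1 dyads a month and would reach 56 in about 7.8 months. So the shortfall is relative to the one 3-month window in section 4 and is not absolute. That also stands, but section 5.3 builds its figures on that window and offers no longer one for small practices.

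The plan sets no cap at 57. It calls 56-57 a goal and an approximate figure, and 1,024 is the commitment. The stop-at-57 results are therefore conditional, and the filling scenario is the more relevant one.

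Section 12.2 discloses equal recruitment as an approximation and calls its ICC conservative, and a loss of about two points is small beside the difference between ICC 0.04 and 0.02. This is fair, but the disclosure does not quantify the inequality, and it does not excuse the pool figure or the per-practice claim in 5.3.

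Finally, Version 9.0 is dated April 2022 and describes final-visit procedures under a December 2020 consent form, so baseline recruitment has probably ended. The correction is then to the record rather than to conduct, and actual cluster sizes should be available for it.

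**Conclusion.** The concern holds. The recruitment pool in section 5.3 is overstated threefold: it is about 1,674 for all 18 practices (1,733 with Westshore annualised), not 5,022. On the stated schedule, six to eight practices cannot recruit 56-57. The lower count annualises Westshore and uses a target of 56; the higher takes the table as printed and a target of 57.

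The total of 1,024 remains feasible, at about 60% of the pool instead of 20%. The cost to power is modest: about two percentage points at ICC 0.04 if larger practices make up the difference, about three if recruitment stopped at 57 each, and about one to three at ICC 0.02.

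These figures assume the volumes in Table 4.1.1, visits spread evenly over the year, the plan's 95% eligibility and 95% participation, one 3-month window per practice, and the same spread of cluster sizes in both arms. The power formula in section 12.2 is not in error; with equal clusters it reproduces.

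**What to change.** In section 5.3:

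- Replace 5,022 with about 1,674 for all 18 practices, and delete the wording that attaches 1,674 to six practices.
- State whether the Westshore count is annualised; if it is, the pool is 1,733.
- Withdraw the statement that a uniform 56-57 per practice is achievable, and align section 7.2.1 with this.

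In section 12.2, restate the power with a design effect that includes the CV of cluster size, using the actual numbers recruited per practice.

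The cost is a text correction and one recalculation. Enrolment, design and the primary analysis do not change.
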